7.1.1 Potential drug-induced liver injury IMP discontinuation criteria

Study participants with potential drug-induced liver injury (PDILI) must be assessed to determine if IMP must be discontinued. In addition, all concomitant medications and herbal supplements that are not medically necessary should also be discontinued.

The PDILI criteria below require immediate and permanent discontinuation of IMP for study participants with either of the following:

- ALT or AST $\geq 8 \times$ ULN
- ALT or AST $\geq 3 \times$ ULN and coexisting total bilirubin $\geq 2 \times$ ULN

The PDILI criterion below requires immediate discontinuation of IMP for:

- Study participants with ALT or AST $\geq 3 \times$ ULN who exhibit temporally associated symptoms of hepatitis or hypersensitivity. Hepatitis symptoms include fatigue, nausea, vomiting, and right upper quadrant pain or tenderness. Hypersensitivity symptoms may include fever (without clear alternative cause), rash, or eosinophilia (ie, $>5\%$).

If a nondrug-related cause for the symptoms can be confirmed, these study participants may resume IMP administration after discussion with the responsible UCB Study Physician, but only when the requirements for rechallenge with IMP as provided in Section 10.6.2.1 are followed.

The PDILI criterion below allows for study participants to continue on IMP at the discretion of the Investigator.

- Study participants with ALT or AST $\geq 5 \times \text{ULN}$ and $< 8 \times \text{ULN}$, total bilirubin $< 2 \times \text{ULN}$, and no eosinophilia (ie, $\leq 5\%$), with no fever, rash, or symptoms of hepatitis (eg, fatigue, nausea, vomiting, right upper quadrant pain or tenderness).

Evaluation of PDILI must be initiated as described in Section 10.6.3, with repeat tests performed in 2 weeks. Upon retest, if ALT or AST values have reduced to $< 5 \times \text{ULN}$, the study participant can continue with the study. However, if ALT or AST remains $\geq 5 \times \text{ULN}$ and $< 8 \times \text{ULN}$ after retest, IMP should be temporarily withheld and study participant should undergo a repeat test in two weeks. If ALT or AST values remain $\geq 5 \times \text{ULN}$ even after the second retest, then the study participant should be permanently withdrawn from the study and should be followed for possible drug-induced liver injury.

If study participants are unable to comply with the applicable monitoring schedule, IMP must be discontinued immediately.

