10.6 Appendix 6: Liver safety – suggested actions and follow-up assessments

The PDILI IMP discontinuation criteria for this study are provided in Section 7.1.1, with the accompanying required follow-up investigation and monitoring detailed below. All PDILI events must be reported as an AE and reported to the study site and Sponsor within 24 hours of learning of their occurrence. Any PDILI event that meets the criterion for potential Hy's Law must be reported as an AE of special interest (see Section 8.2.8.6), and, if applicable, also reported as an SAE (see Section 8.2.8.4).

Evaluation of PDILI consists of the diagnostic testing and continued monitoring included in Table 10-3 (specific tests dependent on laboratory results and corresponding symptoms) and consultation with a local hepatologist (if applicable; discussed in Section 10.6.1). The local hepatologist is the expert usually consulted by the treating physician for assessment and management of potential hepatic disease. This would usually be a hepatologist, but may be a gastroenterologist. Additional investigation and monitoring may be required and adapted based on the diagnosis after the cause of the liver injury/abnormality is confirmed (details in Section 7.1.1.1).

The results of all monitoring, including laboratory testing and other testing, should be made available to the study site and Sponsor.

All initial tests resulting in abnormal hepatic laboratory values need to be repeated, but appropriate medical action must not be delayed waiting for the repeat result.

If tests are done locally for more rapid results, a concurrent sample should also be sent to the central laboratory whenever possible. Medical care decisions are to be made initially using the most rapidly available results, and a conservative approach must be taken if the results from the 2 laboratory tests are significantly different. Data from the local and central laboratory are to be recorded on the applicable eCRF pages.

When IMP is discontinued, all concomitant medications and herbal supplements that are not medically necessary should also be discontinued. In these cases, the Investigator should also consider dose reduction for medically necessary concomitant medication and consider changing any medically required concomitant medication known to be hepatotoxic to a suitable alternative.

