The table for elevated liver function tests (LFTs) will contain data beyond the CTCAE Grade 3 thresholds in order to allow for a more thorough review of elevated LFTs. There will be one table which will list the count and percentage of study participants meeting the below criteria at any time during the study:

- AST: >3xULN, >5xULN, >8xULN, >10xULN, >20xULN
- ALT: >3xULN, >5xULN, >8xULN, >10xULN, >20xULN
- AST or ALT: >3xULN, >5xULN, >8xULN, >10xULN, >20xULN
- Bilirubin: >1.5xULN, >2xULN
- ALP: >1.5xULN

The detailed information of markedly abnormal values criteria can be found in 6.1.7.1.

The following definition of potential drug induced liver injuries (pDILI) will be used:

- [AST  $\ge$  3xULN or ALT  $\ge$  3xULN] and Total Bilirubin  $\ge$  1.5xULN
- [AST  $\geq$ 3xULN or ALT  $\geq$ 3xULN] and Total Bilirubin  $\geq$ 2xULN
- [AST ≥3xULN or ALT ≥3xULN] and Total Bilirubin ≥2xULN in the absence of ALP ≥2xULN (Hy's law)

A table for potential drug induced liver injuries (pDILI) will be presented by treatment group for study participants with at least one post-Baseline liver laboratory assessment. Number and percentage of study participants meeting laboratory criteria for pDILI for at least 1 visit and reporting at least 1 symptom potentially associated with hepatitis or hypersensitivity according to

the Investigator on the pDILI CRF will be presented. Study participants who potentially meet Hy's law criteria at least 1 time during exposure. To be counted as potential Hy's Law, all criteria must be met at the same visit.

Two figures of evaluation of drug-induced serious hepatotoxicity (eDISH) will be created.

- eDISH for maximum Total Bilirubin (y-axis) versus maximum alanine/aspartate aminotransferase (ALT/AST), whichever is higher. Maximum bilirubin and maximum ALT/AST are values of each ULN on a log 10 scale.
- eDISH for maximum Total Bilirubin versus maximum alanine/aspartate aminotransferase (ALT/AST). In this figure, each participant is plotted based on their maximum concurrent total bilirubin (y-axis) and transaminase (ALT or AST, whichever is higher), where maximum concurrent is defined as maximum total bilirubin elevation occurring on or within 30 days after the maximum ALT or AST elevation. The transaminase elevation has to occur first.

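### The SAP's pDILI definition always requires raised bilirubin, so its pDILI table can omit participants who met the protocol's PDILI criteria, including some whose IMP was stopped for PDILI

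*SAP*

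**What the plan says.** Protocol Appendix 6 (10.6) names the governing section: "The PDILI IMP discontinuation criteria for this study are provided in Section 7.1.1". Section 7.1.1 and Table 10-2 then give four criteria, lettered here for reference.

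- **A.** "ALT or AST $\geq 8 \times$ ULN". Table 10-2 sets no bilirubin condition.
- **B.** "ALT or AST $\geq 3 \times$ ULN and coexisting total bilirubin $\geq 2 \times$ ULN". A and B both stand under the sentence "The PDILI criteria below require immediate and permanent discontinuation of IMP for study participants with either of the following".
- **C.** ALT or AST ≥3×ULN in participants "who exhibit temporally associated symptoms of hepatitis or hypersensitivity". IMP stops immediately, and Table 10-2 again sets no bilirubin condition.
- **D.** ALT or AST ≥5 and <8×ULN, bilirubin <2×ULN, no symptoms. IMP may continue at first, but if values stay ≥5×ULN "even after the second retest, then the study participant should be permanently withdrawn from the study".

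SAP 5.6.3.1.1 states "The following definition of potential drug induced liver injuries (pDILI) will be used" and lists three lines:

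1. AST or ALT ≥3×ULN with total bilirubin ≥1.5×ULN.
2. AST or ALT ≥3×ULN with total bilirubin ≥2×ULN.
3. Line 2 without ALP ≥2×ULN (Hy's law).

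The pDILI table is to show the number and percentage of participants "meeting laboratory criteria for pDILI for at least 1 visit and reporting at least 1 symptom", with symptoms taken from the pDILI CRF.

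The same SAP section also plans an elevated liver function table (AST, ALT and either: >3, >5, >8, >10 and >20×ULN) and two eDISH figures. SAP 5.6.2.3.8 plans a hepatic-events table from a MedDRA query and a table of causality scores from the Hepatology Adjudication Committee.

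**The concern.** One term carries two meanings in one study. The protocol uses PDILI for the rules by which IMP is stopped or reviewed. The SAP uses pDILI for a narrower laboratory pattern that always includes raised bilirubin.

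The two will meet in the study report. Protocol 10.6 requires every PDILI event to be reported as an AE, and 7.1.1 requires the eCRF to record the main reason for stopping IMP. A participant could therefore appear in the AE or discontinuation data as a PDILI case while the table headed pDILI shows none. Liver function changes are a prespecified safety topic (protocol 2.3 and 8.2.8.7), and with about 45 participants a single case changes what a reader takes from the table.

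**Working it through.** The plan gives no figure to reproduce here. The check is one of logic, with *x* the ALT or AST value and *tb* total bilirubin, both as multiples of ULN.

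**Step 1: reduce the SAP definition.** Bilirubin ≥2×ULN implies ≥1.5×ULN, so line 2 lies within line 1. Line 3 adds a restriction to line 2. The union of the three lines is therefore *x* ≥ 3 and *tb* ≥ 1.5.

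**Step 2: compare each protocol criterion with that union.**

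| Criterion | Protocol rule | Meets the SAP definition when |
|---|---|---|
| A | *x* ≥ 8 | *tb* ≥ 1.5 only |
| B | *x* ≥ 3 and *tb* ≥ 2 | always |
| C | *x* ≥ 3 with symptoms | *tb* ≥ 1.5 only |
| D | 5 ≤ *x* < 8, *tb* < 2, no symptoms | 1.5 ≤ *tb* < 2 only |

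Three of the four criteria can be met with bilirubin below 1.5×ULN, and then every SAP line fails.

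**Step 3: put cases through both sets of rules.**

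| ALT | Bilirubin | Symptoms | Protocol | SAP laboratory definition |
|---|---|---|---|---|
| 9×ULN | 1.0×ULN | no | A | not met |
| 4×ULN | 2.2×ULN | no | B | met |
| 4×ULN | 1.0×ULN | yes | C | not met |
| 6×ULN, persistent | 1.0×ULN | no | D | not met |
| 6×ULN, persistent | 1.6×ULN | no | D | met |

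**Step 4: see where the unmet cases still show.** In the liver function table, 9×ULN falls in the >3, >5 and >8 rows, 6×ULN in >3 and >5, and 4×ULN in >3. All are plotted in the eDISH figure of maximum values and appear in the laboratory listing. That table uses > where the protocol uses ≥, which matters only for a value exactly on a cut-off: 8.0×ULN appears under >5 but not >8, and 3.0×ULN appears in no row. None of its rows joins an elevation to symptoms.

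**Step 5: read the symptom sentence.** It can be a joint condition (laboratory criteria and a symptom) or two separate counts. If joint, the table is narrower still. If separate, a criterion C participant could appear in the symptom count, but without a link to ALT or AST ≥3×ULN. The text does not settle which.

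**Step 6: check that the protocol's own definition is ready to tabulate.** For criterion D, Table 10-2 adds that the value must be at least twice Baseline; section 7.1.1 does not. The two differ when Baseline exceeds *x*/2, which is 2.5×ULN at the lower cut-off (5/2). Exclusion criterion 24 bars Screening values ≥3×ULN. If Baseline respects the same limit, the two rules can differ only for *x* from 5 to just under 6 (2 × 3).

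**Step 7: size.** One participant in the bimekizumab group is 1/30 = 3.3%, assuming all 30 have a post-Baseline liver assessment and so enter the denominator. The documents give no expected PDILI frequency, so this is the unit of disagreement and not an estimate of how often it will occur.

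**The case against.** The strongest reply is that nothing is lost. Section 7.1.1 sets rules for managing individuals, not an endpoint, and protocol 9.4.1.1 and 9.4.1.3 leave the definitions of safety topics and markedly abnormal laboratory values to the SAP. The one hepatic AE of special interest, potential Hy's law, is carried over with the protocol's laboratory thresholds. Elevations with normal bilirubin appear in the liver function table, the eDISH plots, the listings and, where above 5×ULN, the markedly abnormal table. Events reported as AEs enter the AE tables. The hepatic query and the adjudication committee's table may capture them too.

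Most of this stands, and it rules out three stronger readings.

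- A reader might infer that these participants are counted nowhere, or that hepatic risk as a whole is understated. The outputs just listed contradict that. The committee's selection thresholds are in a charter outside these documents, so its table cannot be assumed to miss them.
- A reader might infer an undeclared departure from the protocol, since SAP Appendix 2 (6.2) is silent. The protocol planned no PDILI tabulation, so there was nothing to declare.
- A reader might take the symptom clause as a firm joint condition. It is ambiguous.

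The reply does not answer the narrower point. The other outputs show values, AE terms or causality scores. None clearly counts participants by the criterion under which the protocol classed them as PDILI, and none clearly links ALT or AST ≥3×ULN to symptoms without a bilirubin condition.

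**Conclusion.** The mismatch is real and confined to the pDILI table. Criterion B is always captured. Criteria A, C and D are missed whenever bilirubin is below 1.5×ULN, and A and C, and D if it persists, can end treatment. The table can then disagree with the AE and discontinuation data, by 3.3 percentage points per participant in the bimekizumab group.

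No primary or secondary efficacy analysis is touched, and the elevations stay visible elsewhere. The conclusion assumes that the pDILI table applies the three SAP lines as written; it holds under either reading of the symptom sentence. It should be corrected because the label is shared, the groups are small and the correction is cheap.

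**What to change.** In SAP 5.6.3.1.1:

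- Keep the three existing lines and label them as bilirubin-based laboratory criteria.
- Add one row to the pDILI table for each protocol criterion, with the protocol's ≥ thresholds: ALT or AST ≥8×ULN; ≥3×ULN with bilirubin ≥2×ULN; ≥3×ULN with symptoms from the pDILI CRF and no bilirubin condition; and ≥5 to <8×ULN with bilirubin <2×ULN and no symptoms.
- Add a row for any protocol PDILI.
- State whether the symptom count is a separate row or a joint condition, and do not require symptoms for the laboratory-only rows.

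Before the ≥5 to <8×ULN row is defined, the sponsor must reconcile protocol 7.1.1 and Table 10-2 on the twice-Baseline condition. Which version should govern is a clinical matter and is not proposed here.

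The cost is SAP wording and a few rows in one table. The liver tests and the pDILI CRF are already collected, and apart from that reconciliation no clinical rule is affected.

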# 5.6.3.2 Vital Signs

# 5.6.3.2.1 Vital Sign Values Over Time

The following vital signs variables will be summarized: systolic blood pressure (mmHg), diastolic blood pressure (mmHg), body temperature (°C) and heart rate (beats/min). The following summaries will be provided for the SS:

• A summary of the absolute and change from Baseline value for each vital sign variable by treatment group and visit during the Treatment Period

# 5.6.3.2.2 Individual Subject Changes of Vital Sign Values

• A summary of the number and percentage of study participants experiencing at least one markedly abnormal value for a vital sign variable during the Treatment Period by treatment.

The detailed information of markedly abnormal values criteria could be found in 6.1.7.2.

# 5.6.3.3 Electrocardiograms

Electrocardiogram data will be analyzed by treatment group and visit for SS.

A summary of the number and percentage of study participants with normal, abnormal ECG results, as determined by the central reader will be presented for all applicable visits through the Treatment Period.

The following ECG variables will be summarized (absolute values and change from Baseline) by visit: QTcF, RR, PR, QRS and QT.

QTc outliers are defined as QTcF values following dosing that are greater than 450 ms or are increases from Baseline greater than 30 ms. QTcF outliers will be highlighted in the data listing and summarized using the following categories:

- Values >450 ms, >480 ms, >500 ms
- Increase from Baseline of >30 ms, increase from Baseline of >60 ms, increase from Baseline of >90 ms
- Values >450 ms and increases of >30 ms. Values >500 ms and increases of >60 ms

The number and percentage of study participants who meet the ECG outlier criteria at any assessment post first dose through the Treatment Period will be summarized.

A separate by-study participant listing of all 12-lead ECG data will be provided based on interpretation from central reader.

#### 5.6.3.4 Assessment and management of TB and TB risk factors

stion A summary of the number and percentage of study participants with negative, positive, and indeterminate IGRA (Interferon-Gamma Release Assay) or Quantiferon Gold Plus results at all applicable visits through the Treatment Period will be presented. If multiple results are present at a visit, only the last result will be used in the summary.

A by-study participant listing of the "Evaluation of signs and symptoms of tuberculosis" questionnaire data and IGRA/Quantiferon Gold Plus results will be provided by treatment group.

A by-study participant listing of the result of chest x-ray for tuberculosis will be provided by treatment group.

#### 5.6.3.5 **Physical examination**

Physical examinations include general appearance; ears, nose, and throat; eyes, hair, and skin; and assessments of the respiratory, cardiovascular, gastrointestinal, musculoskeletal, hepatic, and neurological (including limb reflexes) systems, as well as mental status.

Abnormal results of the physical examination together with details of abnormalities: abnormality clinically significant or not, will be listed by study participants and visit for SS.

#### Patient Health Questionnaire 9 (PHQ-9) scores 5.6.3.6

The PHQ-9 is a multipurpose instrument for screening, diagnosing, monitoring, and measuring the severity of depression. The PHQ-9 scores for depression range from 0 to 27 with higher scores indicating worse state. A score of 5-9 is considered to be minimal symptoms of depression. A score of 10 to 14 is considered minor depression, dysthymia, or mild major depression. A score of 15 to 19 is considered to indicate moderately severe major depression, and a score  $\geq 20$  is considered to be severe major depression.

Change from Baseline in PHQ-9 is derived as post-Baseline score minus Baseline score and will be summarized by treatment group.

PHQ-9 is a Safety parameter described on the Safety Population by actual treatment group. Nevertheless, identification of observable data and implementation of LOCF imputation is done the same way as Efficacy parameters.

A Table presenting the number of study participants with PHQ-9 total score  $\geq 15$  and  $\geq 20$  at all scheduled visits (including Screening, Baseline and each visit through the Treatment Period) and overall at any post-baseline visit will be provided by treatment group using observed case data.

A by-study participant listing of the PHQ-9 questionnaire data will be provided by treatment group including the increase of PHQ-9 scores from the previous visit.

#### 5.6.3.7 Pregnancy testing

Pregnancy testing will consist of serum testing at the Screening. The pregnancy test will be urine at all other visits.

A by-study participant listing of the pregnancy test data will be provided by treatment group.

# 5.6.3.8 Childbearing potential and lifestyle

Childbearing potential and lifestyle will be collected at Screening. A by-study participant listing will be provided for all the study participants screened.

# 5.7 Other Analyses

Pharmacokinetics and immunogenicity analyses are included in this section.

tion

# 5.7.1 Other endpoints and/or parameters

# 5.7.1.1 Pharmacokinetics

Pharmacokinetic variables will be analyzed for all study participants in the PK-PPS who are treated with bimekizumab.

All plasma concentration data will be reported in ug/mL in the tables, figures, and listings. If the dosing for a visit is +/- 21 days out of window then the plasma concentration from that visit and all subsequent visits will be excluded from PK summaries.

If the PK sampling date is >1 day after the dosing date the data point will be excluded from the PK summaries.

All PK concentrations will be listed.

No imputation will be used for missing samples. However, plasma concentrations below the limit of quantification (BLQ) will be set to  $\frac{1}{2}$  of LLOQ in the calculation of the derived statistics (which will include number of values, geometric mean & its 95% CI, geometric coefficient of variation, mean, SD, median, minimum, and maximum). Geometric mean and its 95% CI, geometric CV, mean and SD will be calculated if at least  $\frac{2}{3}$  of the values of interest is above the LLOQ and n>=3; otherwise, only number of values, median, minimum, and maximum will be presented.

All concentrations obtained at the SFU visit will be listed only.

The geometric mean of bimekizumab plasma concentration (with 95% CI) time curve will be plotted on linear and semi-logarithmic scales. The table summary and figure will be repeated by anti-bimekizumab antibody status (positive, negative, missing). The missing group will not be displayed if <5% of study participants are categorized in the missing group.

The ADAb status (positive, negative, or missing) will be considered in a cumulative manner at each time point:

- A study participant will be counted as positive from the first visit at which the study participant achieved a positive ADAb sample result to the end of the treatment period (regardless of any missing/inconclusive or negative ADAb sample result).

- If a study participant has only negative ADAb samples or only one missing/inconclusive sample with negative ADAb samples up to that timepoint, the study participant will be classified as negative.

- Otherwise, the study participant will be classified in the missing ADAb category.

The table summary and figure will also be repeated by neutralizing anti-bimekizumab antibodies (NAb) status: (ADAb negative, NAb positive, ADAb positive/NAb negative, missing; section 5.7.2).

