- ^b The Screening Period will last 2 weeks, but can be extended up to a total of 5 weeks in cases where a laboratory assessment needs to be repeated or to allow washout of prohibited medications.
- ^c For study participants not entering the MAP, the SFU Visit will occur 20 weeks after the final dose of IMP. No SFU will occur for study participants entering the MAP.
- ^d Ensure no significant changes in medical history.
- ^e Includes evaluation of signs and symptoms of active TB and risk for exposure to TB.
- ^f The physical examination will be performed as per protocol.
- ^g Vital signs (sitting systolic and diastolic blood pressure, pulse rate, and body temperature) are to be measured prior to blood sampling, and prior to IMP dosing, where applicable.
- ^h Pregnancy testing will consist of serum testing at Screening. A urine pregnancy test will be administered at all other visits.
- ⁱ Study participants who have evidence of or test positive for hepatitis B by any of the following criteria: 1) HBsAg+; 2) HBcAb+ are excluded. A positive test for HCV is defined as: 1) positive for hepatitis C antibody (anti-HCV Ab), and 2) positive via a confirmatory test for HCV (for example, HCV polymerase chain reaction) are also excluded. Study participants will also be tested for antihepatitis B surface antibody.
- ^j The HIV test results will not be recorded in the eCRF.
- ^k Screening chest x-ray must occur within 3 months prior to the Screening Visit.
- ^l Tuberculosis questionnaire will be required at PEOT.
- ^m The scalp IGA will only be assessed for those study participants with scalp involvement (scalp IGA score >0) at Baseline.
- ⁿ IMP administration is based on randomization.
- ^o The dosing window is ± 3 days relative to the scheduled dosing visit through Week 16.
- ^p Samples will be collected prior to any IMP dosing at a visit.
- ^q If an Unscheduled Visit is conducted due to safety or efficacy reasons, a C-SSRS assessment will be performed with the subject during the visit. If an Unscheduled Visit is conducted for reasons other than safety or efficacy concerns (eg, repeated collection of a laboratory specimen due to collection or analysis issues), a C-SSRS will not be required at these visits.

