8.5 Pharmacokinetics

Blood samples will be collected prior to dosing for measurement of plasma concentrations of bimekizumab at all timepoints described in [Table 1-1](#).

Instructions for the collection and handling of biological samples will be provided by the Sponsor. The actual date and time (24-hour clock time) of each sample will be recorded.

Samples will be used to evaluate the PK of bimekizumab. Samples collected for analyses of bimekizumab plasma concentration may also be used to evaluate safety or efficacy aspects related to concerns arising during or after the study.

Study participant confidentiality will be maintained. At visits during which blood samples for the determination of plasma concentrations of bimekizumab will be taken, 1 sample of sufficient volume can be used.

Drug concentration information that may unblind the study will not be reported to any blinded study personnel as long as the study remains blinded.

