5.1.1.1.5 Definition of Baseline values

A Baseline value for clinical variables is defined as the latest measurement on or prior to the first dosing day of study medication, regardless of the time of the measurement, for the Treatment Period. If a Baseline assessment is taken on the same day as first administration of study medication, it is eligible to be used as the Baseline value, even in the case that the time of the assessment is recorded as taking place after the time of first study medication administration. One exception to this rule is plasma concentration. If Baseline plasma concentration is measured at a time after the first administration of study medication, then it will not be eligible to be considered as a Baseline plasma concentration. Such cases will be discussed with the quantitative clinical pharmacologist.

If a Baseline measurement is missing or not collected, and a Screening value is available, the Screening value will be utilized as Baseline instead. If no measurement is available prior to receiving study medication, then the Baseline value is treated as missing.

Baseline values for component scores should be computed using components from the same visit where the relevant measurements were recorded prior to dosing. For example, if the Screening visit has all of the components, but the Baseline visit is missing one or more components, the Baseline value for the component score should be calculated using the Screening visit values.

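### At Weeks 4, 8 and 12 the SAP's date-only PK rule keeps samples drawn after the injection in concentration summaries that should be pre-dose

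*SAP*

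**What the plan says.** **When samples are drawn.** Protocol 8.5 states: "Blood samples will be collected prior to dosing for measurement of plasma concentrations". The footnote to the schedule of activities (Table 1-1) says the same: "Samples will be collected prior to any IMP dosing at a visit". SAP 6.1.10 gives Baseline and Weeks 4, 8 and 12 as the dosing visits. The concentrations at Weeks 4, 8 and 12 are therefore meant to be troughs, each at the end of a 4-week dosing interval.

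**Which values the SAP leaves out.** SAP 5.7.1.1 has one rule on the timing of the sample relative to the dose: a value is left out of the summaries if the "PK sampling date is >1 day after the dosing date". It compares calendar dates and makes no use of clock time. The other exclusion in that section begins "If the dosing for a visit is +/- 21 days out of window" and concerns a dose given far from its scheduled visit, not the order of sample and injection.

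**What the SAP does at Baseline.** SAP 5.1.1.1.5 generally accepts any assessment on the first dosing day as Baseline, whatever its time, but makes an exception for plasma concentration. "If Baseline plasma concentration is measured at a time after the first administration of study medication", it says, "then it will not be eligible to be considered as a Baseline plasma concentration".

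**What is recorded.** Protocol 8.5 also says: "The actual date and time (24-hour clock time) of each sample will be recorded".

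**The concern.** A rule that tolerates a sample up to one calendar day after the dose does not match a protocol that wants every sample before the dose. A next-day sample is post-dose on its date alone. A same-day sample may fall on either side of the injection, and the rule does not ask which. The SAP shows in its Baseline definition that it knows a post-dose concentration is a different quantity, but it applies that only to the first visit.

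The values that remain feed the geometric means with 95% confidence intervals, the concentration-time plots, and the repeats of both by ADAb and NAb status. SAP 5.7.1.1 allows a geometric mean from as few as three values, provided enough of them are quantifiable, so one mistimed sample in a small antibody group can move the result visibly. At stake is whether a table that readers will take as trough concentrations contains only troughs.

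**Working it through.** The plan gives no figure on this point, so there is nothing to reproduce. The check has three steps.

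**1. Apply the rule as written.** Exclude if (sampling date − dosing date) > 1 day.

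| Sample relative to that visit's dose | Date difference | Baseline | Weeks 4, 8, 12 |
|---|---|---|---|
| Same day, after injection | 0 | Barred as Baseline by SAP 5.1.1.1.5 | Kept |
| Next day | 1 | Barred as Baseline by SAP 5.1.1.1.5 | Kept |
| Two days later | 2 | Excluded by SAP 5.7.1.1 | Excluded |

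Week 16 has no dose, and SFU concentrations are only listed. The gap is therefore at three of the four dosing visits.

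**2. How far might a post-dose value lie from trough?** The documents give no absorption or elimination figures, so this step is illustrative. Assume one compartment with first-order absorption, absorption rate ka of 0.1, 0.3 or 0.5 per day, half-life of 14, 21 or 28 days, and ke = ln 2 / half-life. For a single dose,

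C(t) = ka/(ka − ke) × (e^(−ke·t) − e^(−ka·t)).

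The Week 4 trough is C(28). The Week 12 trough is C(28) + C(56) + C(84). A sample h days after the visit's dose adds C(h) and moves each earlier term to t + h.

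Example at the upper end: ka = 0.5, half-life 14 days (ke = 0.0495), Week 4, h = 1. C(28) = 0.277, C(29) = 0.264 and C(1) = 0.383, so the ratio is (0.264 + 0.383)/0.277, or 2.33 before rounding.

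Over the whole grid:

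| Sample time | Week 4 | Week 12 |
|---|---|---|
| 4 hours after dose | +3% to +28% | +1% to +21% |
| 24 hours after dose | +15% to +133% | +7% to +100% |

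The post-dose to trough ratio f thus runs from about 1.01 to 2.33, and every case is upward. A next-day date can in principle lie almost 48 hours after the dose; at 1.99 days the same model gives +13% to +205%. That would need a dose just after midnight and a sample just before the following midnight, so I do not use it for the range.

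**3. Effect on the geometric mean.** If k of n values are multiplied by f, the geometric mean changes by the factor f^(k/n) = exp(k × ln f / n). Take n = 30, the planned bimekizumab group (Protocol 9.8). The k values, and the subgroup of 5, are assumed.

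| k of n | f = 1.01 | f = 2.33 |
|---|---|---|
| 1 of 30 | exp(0.00995/30): +0.03% | exp(0.846/30): +2.9% |
| 3 of 30 | exp(3 × 0.00995/30): +0.1% | exp(3 × 0.846/30): +8.8% |
| 1 of 5 | exp(0.00995/5): +0.2% | exp(0.846/5): +18% |

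**The case against.** **The PK-PPS may already remove these cases.** PK summaries use the PK-PPS, which requires that a participant have no important deviation affecting the concentration (Protocol 9.1, SAP 4.1.6). Procedural noncompliance is a listed category of important deviation, and such deviations may lead to exclusion from that set (Protocol 9.5). A post-dose sample breaches the protocol, and the criteria for importance sit in a separate document that is not available here. It is therefore too strong to say that every such value will certainly be summarized. But the set works on participants, not single samples. Neither document names post-dose sampling as an important deviation, and SAP 5.7.1.1 still gives its own sample-level timing rule. The route might catch some cases but cannot be relied on to close the gap.

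**The effect is small beside the sampling error.** This is fair. Assuming a between-participant geometric CV of 30% to 50%, the upper 95% limit lies exp(2.045 × √ln(1 + CV²)/√30) − 1, or about 12% to 19%, above a geometric mean of 30 values. A few same-day samples would be lost within that. All concentrations are listed, so an affected value can be found.

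**The PK exclusion text was revised on purpose.** The SAP version history records an update in Amendment 1. That shows it was considered, but the SAP gives no reason for the one-day allowance.

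**Stronger readings that the documents do not support.** Because this is a bridging study, a reader might infer that these summaries will be compared with exposure in earlier studies. No section plans that: Protocol 4.2 rests PK comparability on a dedicated Phase 1 study, and Protocol 9.4.2 plans descriptive statistics, with any model-based work reported separately. A reader might also assume that a post-dose value is typically 1.5 to 3 times trough. The documents give no such multiplier, and every 4-hour case above falls below 1.5. Nor does the 21-day dosing rule add to this point: it addresses a different deviation, and it removes the affected visit and all later ones.

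**Conclusion.** The point holds for Weeks 4, 8 and 12. It is an explicit rule that admits values the protocol did not intend, rather than a missing detail. Any bias is probably upward, as in every modelled case. The sizes worked out above rest on an assumed model and on an assumed number of mistimed samples; the documents supply neither, so the real size is unknown. The small antibody-status groups are the most exposed.

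The reach is narrow. PK concentration is a tertiary endpoint summarized descriptively. The co-primary analyses, power and type I error are not touched, nor are the Baseline and Week 16 concentrations. This is a desirable correction, not an essential one.

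**What to change.** Extend the Baseline principle in SAP 5.1.1.1.5 to the later dosing visits. In SAP 5.7.1.1, replace the one-day rule with wording to this effect: at Weeks 4, 8 and 12, any sample taken after that visit's dose, judged by the recorded sample and dose times, is excluded from the PK summaries and figures but still listed with a flag; where the dose time is not available, any sample dated after the dosing date is excluded.

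The fallback is needed because only the sample time is documented as recorded. SAP 5.1.1.1.5 implies a time for the first dose, but neither document states that dose clock times are captured at Weeks 4, 8 and 12, so this should be confirmed with data management. Under the fallback, same-day post-dose samples could still get through, but next-day samples could not.

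The cost is a short edit to the SAP and its matching program step, and perhaps a few lost values.
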